If the sample is imbalanced with respect to team type (CIN / CP, CLA, children with disabilities) within the local authority, we will re-randomise (setting a new seed). We take imbalance to be the proportion of teams of that type within the local authority assigned to the intervention to be greater than 0.75 or less than 0.25 (i.e. $\frac{3}{4}$ or $\frac{1}{4}$ teams) except where there is only one team of that type in the local authority.

We will also report the mean proportion of social workers to family support workers, and the mean proportion of permanent staff to agency staff, by treatment allocation but will not re-randomise if there is imbalance in treatment allocation on these variables. With a relatively small number of teams to allocate, we have decided to prioritise team type (within the local authority) to enable us to compare the impact of the programme on these subgroups.

Data collection

We have several data collection methods:

Impact evaluation

- Children and young people:
 - administrative data to measure children's social care involvement
- Social workers:
 - online survey to measure self-efficacy, stress
 - administrative data to measure sickness absence
- Foster/kinship carers:
 - online survey to measure self-efficacy

⁷ Due to a delay of the required data from Oxfordshire County Council, the randomisation was conducted for the three other local authorities first, and the teams from Oxfordshire County Council were allocated separately.

Sample size / MDES calculations

		MDES (Proportion of a Standard Deviation)
MDES		0.127
Proportion of variance in child's outcome explained by:	Child covariates (including baseline measure)	0.8
	Social Worker team covariates	0.1 (3 covariates)
Intraclass correlations (ICCs)	Team	0.03
Alpha		0.05
Power		0.8
One-sided or two-sided?		Two-sided
Level of intervention clustering		Social worker team
Average cluster size		150 children in each team
Sample Size (children)	Intervention	4500
	Control	4500
	Total	9000
Sample Size (teams)	Intervention	30 (15 per local authority)
	Control	30 (15 per local authority)
	Total	60

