Children are clustered into sibling groups, households (e.g. with other children in foster care) and caseloads (i.e. a group of children have the same social worker) and social worker teams. Because of this clustering, observations within one group (sibling group, household etc) may be more similar with each other on various characteristics compared with observations in other groups violating the assumption of independence. When data is structured in this way, the estimation of the treatment effect remains unbiased but the standard errors may be misspecified, leading to problems with inference. To correct for this, standard errors will be clustered at the level of randomisation, the social worker team level, in line with WWCS statistical guidance. This also accounts for correlations between observations at lower levels of nesting.

Handling non-compliance

If CYP are transferred to another team (e.g. due to a change of status), it is possible that the team to which they are transferred was ineligible for participating in the programme or had a different intervention / comparator group allocation. If a social worker or family support worker changes teams, it is possible that their new team had a different intervention/ comparator allocation. For all our analysis, we will conduct intention to treat analysis where a CYP is considered as treated if they are / were supported by a social worker who is a member of an intervention team at the point they entered the sample (either at randomisation or when their case started), irrespective of their use of Kitbag.

Multiple Comparison Adjustments

We will adjust for multiple comparisons within the secondary outcomes using Hochberg's step-up procedure, as per WWCS statistical guidance.

Regression specification

For social workers, family support workers and foster carer outcomes:

$$Y_{ict13} = \beta_0 + \beta_1 D_c + \beta_{2:4} A_c' + \beta_5 Y_{ict0} + \beta_{6:k+6} X_i' + \beta_{k+6:k+11} M_c' + \epsilon_c$$

Where:

- Y_{ict13} is the dependent variable for individual i , team c at the end of the trial, $t13$. β_0 is the intercept
- D_c is the treatment variable
- A_c is a vector of the local authority fixed effects
- Y_{ict0} is the "pre" outcome of individual i in team c , at their "pre" data collection point, $t0$
- X_i' is an $N \times k$ matrix of characteristics of individual i
- M_c' is an $N \times 5$ matrix of characteristics of team c
- ϵ_c is the error term clustered at the team level c

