Focus groups	T10-T12	
We will send information about the focus groups to the practitioners via the Kitbag super lead and then purposively sample aiming for a heterogenous sample of practitioners from different team types and of different roles.
 
For the focus group discussions for the super leads, all will be invited to attend.

Interviews (n=16)	T10-T12	
Children: Practitioners who attend the focus group discussion will be asked to identify children on their caseload who may be open to participating.
 
Foster carers: the Kitbag leads in the fostering teams will be asked to send information about the interviews to the foster carers. We

		will purposively sample aiming for a heterogenous sample of foster carers of children of different ages.
Survey (assume 10% response rate)	T1 T13	A survey will be shared with all staff (i.e. no sampling) across intervention and comparator teams: 
 • Social workers and family support workers (includes Kitbag Leads) • Inhouse foster carers (the survey will be adapted slightly for this group) • Team Managers
Observations of workshops (n=4)	T3-T4	A researcher or research assistant will observe at least one workshop per local authority.

Analysis

Qualitative data preparation and analysis of interview and observational data

Interviews will be recorded, transcribed and pseudonymised prior to analysis. Qualitative analysis of interview and observational data will use NVivo software and follow a thematic analysis approach. This will involve data familiarisation, checking accuracy of transcription, labelling the data with descriptive codes and developing themes which describe patterns across the data to answer the pre-specified research questions. Analysis will look for patterns, consistencies and inconsistencies across different informants and time points that might be informative for the research questions.

The following steps will be taken to ensure rigor in the analysis and reporting of qualitative data:

- Confidence that the findings are an accurate reflection of participant experience will be ensured through presentation of examples of participant responses using quotes, and triangulation between different informants and data collection methods.
- The degree to which findings are transferable to other contexts will be considered through detailed description of contextual factors, and collection of data from a range of informants to gather a range of perspectives.

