- Transparent reporting of the research and analysis process will ensure the study methods are clear and repeatable.
- When interpreting findings, consideration will be given to contrasting and inconsistent accounts.
- Qualitative data analysis will be overseen by WWCS's Senior Qualitative Researcher.

Quantitative analysis of survey and administrative data

Quantitative data will be analysed descriptively, in order to present characteristics of delivery and acceptability. The results will be triangulated with the qualitative findings by looking for consistencies and inconsistencies between the different data sources.

Cost evaluation

Whose costs

We consider the costs from the perspective of the local authorities if they were to implement the programme themselves. We shall report the total costs for each local authority and the costs per family (total costs / (total caseload for treated teams at the beginning of the intervention + the total caseload who start within the intervention period)).

We do not consider costs to families. The use of the Kitbag will be during their usual sessions with social workers and family support workers so there is no additional cost to them in terms of time or otherwise.

What costs

Given that the programmes team of WWCS is funding the programme, we shall request the budget submitted to them from the intervention developers. We shall include all costs related to the provision of the programme (but not the development) broken down by the following categories:

- **Kitbags** for social workers and family support workers in the treated teams. Kitbags for foster carers and kinship carers of the children supported by these teams. An additional 15% of the total Kitbags required to allow for staff turnover (permanent staff can take their Kitbag with them) and an additional 10% for foster / kinship carers (due to placement change and / or carer turnover).
- **Access to Kitbag Online** (if a licence is required)
- **Distribution of Kitbags**
- **Workshops by the intervention developers**
- **Support for using Kitbags other than the workshops**
- **Other costs associated with delivering the programme**

Additionally, we shall ask the local authorities (via a survey to the local authority lead contact) if they incurred any additional costs associated with the programme e.g.:

- **Resources:** the replacement of lost or empty items from Kitbags; additional resources for the workshops

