- **Personnel:** the cost of hiring agency workers to conduct day-to-day work so that social workers / family support workers could attend the workshops (if applicable)
- **Administration costs:** the cost of hiring additional staff to administer the programme

The costs will be reflective of the current context of Covid-19 restrictions. In some cases, this is likely to increase the costs e.g. distribution, and in other circumstances, it's likely to decrease the costs e.g. virtual workshops instead of in-person workshops.

Where there is additional work required but not sufficient to hire an agency worker or another member of staff, we shall report the additional time commitment in hours over the course of the year for the staff affected.

As well as these costs incurred over the duration of the programme, we shall report prerequisites (anything the local authority needed to run the programme but may already have e.g. laptops) and expected ongoing costs. Costs associated with the development of the programme and the evaluation e.g. the collection of data will be excluded.

Valuing benefits and disbenefits

Although administrative outcomes aren't the outcomes of most interest, we only include the administrative outcomes when valuing benefits as these are the benefits that are "cashable" to local authorities:

- De-escalation in children's social care status as a benefit
- Escalation in children's social care status as a disbenefit
- Number of social worker sick days averted (estimated by the coefficient on treatment in the regression of the number of days attended on treatment and covariates)

For the impact evaluation, we code de-escalation and escalation as a single outcome. But because there are different costs associated with each movement, we shall separately estimate the impact of Kitbags on the likelihood of moving between different levels of CSC intervention. For each movement, we calculate the total monetised benefit:

- Unmonetised benefit = ATE (i.e. the coefficient on the treatment dummy) x number children randomised to the intervention group
- Monetised benefit: total unmonetised benefit x cost (averted) / child

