The outcomes do not double count any benefits and we only include outcomes that are significant at the 5% level. We request data from the local authorities on the average costs of supporting a child at each level of CSC intervention and use this to determine the "cost (averted)" value. Whilst placement costs vary, we use an average for simplicity. We sum the monetised benefits and disbenefits to arrive at a net benefit.

We do not monetise the other outcomes such as improved behaviour amongst children and young people. This is not to say that these outcomes aren't valuable but simply that there's less agreement on how to put a monetary value on these outcomes. We report a list of outcomes that are significant.

Discounting

Given that all the benefits and costs occur within the same financial year, we do not discount any of the benefits or costs.

Reporting

We report the benefit-cost ratio, and the net present value per child.

Ethics & Participation

An ethics application for this evaluation was submitted to WWCS's research ethics committee on 25th February 2021 with a favourable opinion given on 23rd March 2021.

Consent procedures

Information sheet contents

The information sheets will be tailored to the participant group and will detail the purpose of the project, why they have been invited to take part, what will happen if they take part, whether they have to take part, the possible risks, the possible benefits, the data handling, confidentiality and data protection, the right to withdraw their consent, how the project is funded, what will happen to the results of the project, contact details if they wish to ask further questions.

Social workers

Data collection from social workers will be via an online survey. The first page of the survey will be an information sheet and consent elicitation.

Impact Evaluation: Secondary Data Collection

Children and young people

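### The cost measure labelled per family divides by caseload, which the protocol elsewhere uses for children, so it most naturally gives a cost per child

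*Protocol*

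**What the plan says.** Under Cost evaluation, Whose costs, the protocol takes the perspective of a local authority running the programme itself. It commits to total costs for each authority and to a unit cost, given as a formula: "costs per family (total costs / (total caseload for treated teams at the beginning of the intervention", to which it adds "the total caseload who start within the intervention period". That subsection does not say what a unit of caseload is, and gives no count of families.

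Elsewhere, caseload refers to children. The Standard errors paragraph of the analysis plan explains "caseloads (i.e. a group of children have the same social worker" and, in the same sentence, says "Children are clustered into sibling groups, households (e.g. with other children in foster care". In the Data collection schedule, practitioners are "asked to identify children on their caseload who may be open to participating".

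The later parts of the Cost evaluation section use the child as the unit. Under Valuing benefits and disbenefits, the treatment effect is multiplied "x number children randomised to the intervention group" and then by a cost averted for each child. Under Reporting: "We report the benefit-cost ratio, and the net present value per child".

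**The concern.** The label and the denominator of the unit cost do not appear to be in the same unit. If caseload counts children, dividing by it gives a cost per child whatever the label says. Since the protocol itself expects siblings and shared households, there are fewer families than children, and the printed figure would be lower than a true cost per family.

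Two uses of the figure would suffer. An authority budgeting by number of families would set aside too little. A reader placing a cost per family beside a net present value per child would assume that a conversion between the two units had been made, when none is planned.

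**Working it through.** The protocol states no value for the cost per family, so there is no figure to reproduce. The check is of units.

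**Inputs**
- C, total cost: not given.
- K, children on the caseload of treated teams. For scale only, the Sample size / MDES table has "150 children in each team" and 30 intervention teams: 30 × 150 = 4500, which matches the table's own intervention total. The denominator under Whose costs need not equal this number.
- m, mean number of children per family on the caseload: not given. The Standard errors paragraph implies m > 1, because it describes sibling groups and shared households. The values below are assumptions.

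**Formulas**
- The protocol's ratio, with caseload read as children: C / K, a cost per child.
- Number of families: K / m.
- Cost per family: C / (K / m) = m × C / K.
- Relative shortfall of the protocol's ratio: 1 − (C / K) / (m × C / K) = 1 − 1/m. Neither C nor K affects it.

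**Results, with K = 4500 for illustration**

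| Assumed m | Families, 4500 / m | Shortfall, 1 − 1/m |
|---|---|---|
| 1.0 | 4500 | 0% |
| 1.3 | 3462 | 23% |
| 1.5 | 3000 | 33% |
| 2.0 | 2250 | 50% |

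**Population behind each figure**
- Whose costs: the caseload of treated teams at the start plus everyone who starts during the intervention. No age limit and no cut-off date is stated.
- Participants, Children and young people: eligible children are aged 4 to 18, with a case open in May 2021 or opening up to December 2021.
- Reporting of the net present value: per child, with no denominator stated. The nearest child count is the one used to scale the benefits.

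So the two economic figures carry different unit labels and may also rest on different sets of children.

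**The case against.** The strongest reply is that the protocol never defines caseload for costing purposes. The wording under Standard errors is a parenthesis about clustering, and the Data collection schedule is about finding interviewees. The Contextual Factors Analysis section warns that caseload numbers may be defined differently from one authority to another. This stands in part: the protocol does not establish that the formula must yield a cost per child, only that this is the natural reading. It does not rescue the label. The warning does not say that any authority counts families, and if one did, the ratio would mix units across sites.

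A second reply is that the protocol uses family loosely. Its opening summary table has a row for children and families and fills it with a count of children only. The formula is also printed next to its label, so a careful reader can see what was divided by what. That is fair, and it makes this a wording matter rather than a wrong calculation.

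Three stronger readings are tempting but unsupported:
- A reader might infer that the unit cost and the net present value share one denominator under two labels. The protocol gives no denominator for the net present value, and the populations may differ.
- A reader might take 23% to 50% as the size of the error. Those percentages come only from assumed family sizes; the shortfall is zero if every family has one child on the caseload.
- A reader might think the economic conclusions are affected. The unit cost does not enter the monetised benefit, the benefit-cost ratio or the net present value.

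**Conclusion.** The point holds as a minor unit inconsistency. A ratio labelled per family has a denominator that most naturally counts children, while the rest of the economic analysis works per child. The direction of the shortfall rests on two things: caseload meaning children, as it does elsewhere in the protocol, and some families having more than one child on the caseload, as the protocol acknowledges. The size, 1 − 1/m, cannot be fixed from the protocol. No stated figure is wrong, and the consequence is confined to one descriptive cost figure given to local authorities, which also receive total costs and a breakdown by category.

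**What to change.** - Under Whose costs, relabel the measure as cost per child.
- State that caseload means distinct children, counted in the same way in all four authorities. The word distinct matters because the outcome definition allows a child's case to close and another to open, so a count of starts could include the same child twice.
- State the denominator of the net present value per child and use that same count for both figures, saying whether the age range and the December 2021 limit apply.
- If a per-family figure is wanted as well, divide by the number of distinct families or households in the treated teams' caseload.

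The first three changes are wording, plus agreement with the authorities on one counting rule. The per-family figure would need a pseudonymised family or household identifier in the data request.

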- The appointment of a “Kitbag Super Lead” to lead the adoption of Kitbags across the local authority, and two “Designated Kitbag Leads” in each team (in the intervention group only) to support colleagues in their team to use Kitbags. The Super Lead coordinates the project overall, getting the necessary buy-in and arranging the logistics of distributing Kitbags. In this case, they also play a major role in setting up the evaluation. The Kitbag Leads are appointed on the basis of an expression of interest - some of the local authorities have chosen for one of the Kitbag Leads to be a team manager or senior practitioner.
- Monthly workshops for Designated Kitbag Leads facilitated by IFF/UoS to support them in their role of encouraging uptake and use of Kitbag by social workers and foster carers within their local authorities.
- Support by Designated Kitbag Leads to social workers and foster carers to provide support to use the Kitbags and facilitate sharing of ideas for how to use the Kitbag. Due to time constraints, it is expected that the support takes place in routine team meetings. The Designated Kitbag Leads in the fostering teams support their colleagues to support foster carers.
- Social workers and family support workers completing recording sheets as a space to reflect on using the Kitbag as part of direct work.

A Kitbag contains:

- Aromatic oil
- Timers: to time mindfulness exercises and in conversations for people to take turns with equal amounts of time
- Feelings cards: which open up a way to describe and share feelings
- A talking stick: which encourages listening and taking turns for people to speak and others to listen with respect
- Animal cards: cards with a picture of an animal and an associated quality e.g. love, communication etc. designed to encourage affirmation and empathy.
- Presence cards: which feature mindfulness exercises
- A “Wonder journey”: a story which acts as a visualisation and relaxation exercise
- Finger puppets: to enable role play and for soothing

Kitbag Online replicates elements of the Kitbag in an online form, for example, the user can display all of the animal cards and click on each card to turn it over and reveal the characteristic associated with the animal.

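### Cost evaluation: staff days gained count as a benefit without a check that cover was saved, but staff days spent count as a cost only if someone was hired

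*Protocol*

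**What the plan says.** All of this is in the protocol's Cost evaluation section, except the description of the programme.

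- **Perspective (Whose costs):** "We consider the costs from the perspective of the local authorities if they were to implement the programme themselves".
- **Staff time as a cost (What costs):** two personnel items enter in money. One is "the cost of hiring agency workers to conduct day-to-day work so that social workers / family support workers could attend the workshops (if applicable"); the other is the cost of extra staff hired for administration. Where the additional work is "not sufficient to hire an agency worker or another member of staff, we shall report the additional time commitment in hours" over the year for the staff affected. No price is attached to those hours.
- **Staff time as a benefit (Valuing benefits and disbenefits):** the list includes "Number of social worker sick days averted (estimated by the coefficient on treatment in the regression of the number of days attended"), with covariates in that regression. The reason given for the choice of benefits is that "we only include the administrative outcomes when valuing benefits as these are the benefits that are" cashable to local authorities. Later text in that subsection admits only outcomes significant at the 5% level.
- **Summary measures (Reporting):** "We report the benefit-cost ratio, and the net present value per child".
- **Staff input required (Intervention and Theory of Change, What):** a Super Lead in each authority, two Designated Leads in each intervention team, "Monthly workshops for Designated Kitbag Leads facilitated by IFF/UoS", support by Leads to colleagues, and recording sheets.

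**The concern.** An authority that runs the programme itself supplies its own staff time, so that time falls within the stated perspective. A salaried worker who attends a workshop adds nothing to the payroll, and a salaried worker who is not off sick normally takes nothing off it. Cash moves only if cover is hired in the first case or avoided in the second. The plan applies that cash test to the cost and not to the benefit.

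The programme's cost is therefore understated relative to the way its staff-day benefit is counted. What is at stake is the pair of headline economic figures, the ratio and the net present value per child. No primary or secondary effect estimate is affected.

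**Working it through.** The protocol gives no ratio, wage, sick-day value or workshop length, so there is no figure of its own to reproduce. The check has three parts.

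**1. The two rules side by side**

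| | Staff day spent on the programme | Staff day gained (sick day averted) |
|---|---|---|
| Condition for entering in money | Agency cover or additional staff hired | Treatment coefficient significant at 5% |
| Check that cash moved | Yes, by construction | None stated |
| If the condition fails | Reported in hours, unpriced | Dropped |

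The gained days come from the days-attended outcome. Under Outcome measures (Days attended), leavers count as absent every day after leaving, and absence may include holidays and parental leave. The coefficient can therefore also contain retention of staff, whose days the authority pays for.

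**2. Size of the unpriced time (illustration)**

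Inputs from the protocol:
- 30 intervention teams (Sample size / MDES calculations)
- 2 Leads per intervention team and monthly workshops (Intervention and Theory of Change), taken as 12 over the 12-month period
- 300 social workers and family support workers in intervention teams (Table 2: 33 + 28 + 120 + 119 = 300)

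Assumptions: full attendance, 1 to 2 hours per workshop, a 7.4-hour day.

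- Attendances: 30 × 2 × 12 = 720
- Hours: 720 × 1 = 720, up to 720 × 2 = 1,440
- Days: 720 / 7.4 = 97, up to 1,440 / 7.4 = 195
- Per intervention worker: 97.3 / 300 = 0.32, up to 194.6 / 300 = 0.65 day

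This leaves out Super Lead time, Lead support to colleagues and Leads in the fostering teams. Incomplete attendance would lower it.

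**3. How large a sick-day effect must be to enter the ratio**

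Assume 300 staff per arm, with no clustering and no covariates. The smallest significant estimate is then 1.96 × SD × √(2/300) = 0.160 × SD.

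- *Leavers included.* The protocol expects about 80% of staff to remain at T13, so 20% leave. Assume 230 working days and leaving times spread evenly over the year. Mean days lost = 0.2 × 115 = 23. Mean square = 0.2 × 230² / 3 = 3,527. SD = √(3,527 − 23²) ≈ 55 days. Threshold ≈ 8.8 days.
- *Leavers ignored.* With an assumed SD of 10 days, the threshold ≈ 1.6 days.

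Clustering by team would normally raise these thresholds and covariates would lower them. Workshop time of 0.32 to 0.65 day is about 4% to 7% of the first threshold (0.32/8.8, 0.65/8.8) and about 20% to 41% of the second (0.32/1.6, 0.65/1.6).

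**The case against.** The strongest reply has four parts.

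- **The 5% filter.** A sick-day effect as small as the workshop time would rarely be significant, so it would rarely enter the ratio. If it does not enter, no staff-day gain is valued and a cash-only costing remains. This stands. A reader might infer that workshop attendance alone could wipe out the sick-day benefit. Part 3 of the working does not support that for workshop time, and other staff time is not quantified in the protocol.
- **No sick-day price is stated.** The monetisation formula is written for children's movements between levels of care. If a sick day were valued by cover saved, the two sides would match. That is a possible reading, but the text lists sick days averted without that condition, and nothing in it restricts the count to days that would have been covered.
- **The hours are reported.** They are unpriced, not hidden, and a reader could price them. The plan also costs additional staff who are hired, not only agency cover. Both points are correct, but the ratio and net present value would still omit the other hours.
- **Direction.** A reader might infer that the whole ratio is biased in favour of Kitbag. The protocol does not support this. Outcomes such as behaviour are left unmonetised and non-significant benefits are dropped, and both choices can work against the programme.

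Lead support is also expected to take place in routine team meetings, where it may displace other work rather than add hours. The total of unpriced time is therefore uncertain.

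**Conclusion.** The inconsistency is in the stated rule and holds. Staff time spent must pass a cash test to be counted in money. Staff time gained need only be statistically significant. For this component, programme cost is understated; nothing follows about the net direction of the ratio.

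Under the assumptions above, Lead attendance at workshops alone leaves about 97 to 195 staff days unpriced, or 0.32 to 0.65 day per intervention worker. Workshop length, attendance and day length are the uncertain inputs. Any sick-day benefit large enough to be counted would probably exceed this, so the omitted workshop time would reduce it by a fraction that depends on the unknown spread of days attended. The point deserves correction in the cost section and does not touch the trial's effect estimates.

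**What to change.** Choose one basis and apply it to both sides.

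- **Staff-time basis:** state one unit cost for a staff day. Apply it to sick days averted and to the additional programme hours the plan already undertakes to report, excluding time spent on the evaluation. Include those hours in the costs of the ratio and the net present value.
- **Cash-only basis:** keep the present cost rule, and count sick days averted only where paid cover was saved.

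Show the cash-only and the staff-time-inclusive figures side by side.

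The cost is modest. A unit rate must be defined and obtained from the authorities, and the source of the reported hours should be named, because the section does not say how they will be collected. The cash-only basis also needs information on whether cover was saved. The ratio will be somewhat less favourable than under the present rule.
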